9.1.2 Withdrawal of informed consent

Patients themselves or parents/ legal guardians may voluntarily withdraw consent for their child to participate in the study for any reason at any time. Withdrawal of consent from the study is defined as when a patient does not want to or the patient's parent/ legal guardian does not want their child to:

- Participate in the study anymore and
- Does not want any further visits or assessments and
- Does not want any further study related contacts and
- Does not allow analysis of already obtained biologic material. In this situation, the investigator must make every effort (e.g. telephone, e-mail, letter) to determine the primary reason for the patient's or parent's/ legal guardian's decision to withdraw their consent and record this information. Study treatment must be discontinued and no further assessments conducted, and the data that would have been collected at subsequent visits will be considered missing.

Further attempts to contact the parent/legal guardian are not allowed unless safety findings require communicating or Follow-up.

All efforts should be made to complete the assessments prior to study withdrawal. A final evaluation at the time of the patient's study withdrawal should be made as detailed in the assessment table. Where consent to the use of personal and coded data is not required, patient

therefore cannot withdraw consent. They still retain the right to object to the further use of personal data.

Novartis will continue to retain and use all research results (data) that have already been collected for the study evaluation.

9.1.3 Lost to follow-up

For patients whose status is unclear because they fail to appear for study visits without stating an intention to discontinue or withdraw, the investigator must show "due diligence" by documenting in the source documents steps taken to contact the patient, e.g. dates of telephone calls, registered letters, etc. A patient should not be considered as lost to follow-up until due diligence has been completed or until the end of the study.

9.1.4 Early study termination by the sponsor

The study can be terminated by Novartis at any time.

Reasons for early termination:

- Unexpected, significant, or unacceptable safety risk to patients enrolled in the study
- Decision based on recommendations from applicable board(s) after review of safety data
- Discontinuation of study drug development

In taking the decision to terminate, Novartis will always consider patient welfare and safety. Should early termination be necessary, patients must be seen as soon as possible. The investigator may be informed of additional procedures to be followed in order to ensure that adequate consideration is given to the protection of the patient's interests. The investigator or sponsor depending on local regulation will be responsible for informing IRBs/IECs of the early termination of the trial.

9.2 Study completion and post-study treatment

Study completion is defined as when the last patient finishes their Study Completion visit, and any repeat assessments associated with this visit have been documented and followed-up appropriately by the Investigator, or in the event of an early study termination decision, the date of that decision.

Patients that completed the study or prematurely discontinued will not be given further access to the investigational treatment.

The investigator must provide follow-up medical care for all patients who completed or prematurely withdrawn from the study, or must refer them for appropriate ongoing care.

All treated patients should have a safety follow-up call conducted 30 days after last administration of study treatment. All SAEs reported during this time period must be reported as described in Section 10.1.3. Documentation of attempts to contact the patient should be recorded in the source documentation.

10 Safety monitoring and reporting

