3.1.1 Study design

This is an open-label, two-period, single-sequence, crossover study to assess the pharmacokinetics, safety and tolerability of single inhaled doses of mometasone furoate (MF) when administered alone via MF Twisthaler[®] (TH) or as an indacaterol acetate/MF fixed dose combination (QMF149) via the Concept 1 (C1) device in ≥ 6 to <12 year old asthma patients. The study includes two open-label single-dose treatment visits. On the first treatment visit (Day 1) patients receive a single inhaled dose of 100 µg MF administered via the Twisthaler[®] device. On the second treatment visit (Day 6) patients receive a single inhaled dose of 75/40 µg indacaterol acetate/MF fixed dose combination (QMF149). Both treatments are in addition to their rescue medication and potentially SoC asthma therapy (excluding MF and indacaterol acetate).

Patients currently taking low-dose ICS asthma medications other than MF can enroll in the study. However, since the patients will be provided MF or QMF149 as part of study treatment on Day 1 and Day 6 respectively, patients should be instructed not to take low-dose ICS medication on the 2 treatment days.

The study will include the following:

- A screening period of up to 14 days
- Two single-dose treatment periods separated by a 4-7 day washout period (4 days is minimum washout)
- A 30-day investigational drug-free follow-up period

4 Rationale

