6.1.4 Treatment arms/group

All patients will receive an inhaled single dose of MF TH 100 μg on Day 1 and an inhaled single dose of QMF149 75/40 μg on Day 6 .

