6.2.1 Concomitant therapy

All medications, procedures, and significant non-drug therapies (including physical therapy and blood transfusions) administered within 30-days prior to enrolment and after the patient was enrolled into the study must be recorded on the appropriate Case Report Forms.

Each concomitant drug must be individually assessed against all exclusion criteria/prohibited medication. If in doubt, the investigator should contact the Novartis medical monitor before

assigning the study treatment to patient or allowing a new medication to be started. If the patient is already enrolled, contact Novartis to determine if the patient should continue participation in the study.

The investigator must instruct the patient to notify the study staff about any new medications he/she takes after the patient was enrolled into the study. All medications, procedures and significant non-drug therapies (including physical therapy and blood transfusions) administered after the patient was enrolled into the study must be recorded in the concomitant medications / significant non-drug therapies e-CRF.

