Period Visit Name Days	Screening Screening -14 to -1	Treatment		Early Termination	Follow Up
		Day 1	Day 1 Day 6 1 6 -0 +3	-	Day 36 ¹ 36
		1			
Obtain parental Informed Consent / patient assent (if applicable)	Х				
Register Patient and Visit in IRT	Х	Х	Х		
Demography	Х				
Inclusion / Exclusion criteria ²	Х	Х			
Medical history/current medical conditions	Х				
Prior/ concomitant medication review	Х	Х	Х	Х	
AE/SAE	Х	Х	Х	Х	Х
Device training	Х	Х	Х		
Physical Examination	Х	Х	Х	Х	
Hematology	Х		Х	Х	
Clinical Chemistry	Х		Х	Х	
Urinalysis	Х		Х	Х	
Pregnancy and assessments of fertility ³	Х	Х	Х	Х	
Electrocardiogram (ECG)	Х		Х	Х	
Vital Signs	Х	Х	Х	Х	
Height and Weight	Х				
Telephone patient/parent/legal guardian in advance of study visit ⁴		х	х		
Dose administration		Х	Х		
PK blood collection		Х	Х		
Snack/Meal ⁵		Х	Х		
Safety Follow up Call					Х

Confidential

Novartis Clinical Trial Protocol (Version No. 01)

Page **35** of **63** Protocol No. CQMF149G2203

Period	I Screening	Treatment		Early Termination	Follow Up			
Visit Name	e Screening	Day 1	Day 6		Day 36 ¹			
Day	-14 to -1	1	6 -0 +3	-	36			
 ^X Assessment to be recorded in the clinical database or received electronically from a vendor ¹ This would occur 30 days after last study treatment. ² Inclusion/Exclusion evaluation at screening is recorded in CRF. Inclusion/Exclusion prior to dosing on Day 1 should be documented in source. ³ Serum pregnancy test at screening (approximately 0.5 mL blood volume) and urine pregnancy test during treatment visits ⁴ Patient/Parent/Legal Guardian should be reminded to withhold controller ICS on Days 1 and 6 study visits AND to withhold rescue medication within 8 hours of Days 1 and 6 study visits. ⁵ Patients should consume a small snack approximately 1 hour post-dose and a meal approximately 4 hours post-dose. Snack and meal times should be recorded on the CRF and food content should be recorded in source documentation. 								

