10.1 Definition of adverse events and reporting requirements

10.1.1 Adverse events

An adverse event (AE) is any untoward medical occurrence (e.g. any unfavorable and unintended sign [including abnormal laboratory findings], symptom or disease) in a patient or clinical investigation patient after providing written informed consent for participation in the study. Therefore, an AE may or may not be temporally or causally associated with the use of a medicinal (investigational) product.

In addition, all reports of intentional misuse and abuse of the product are also considered an adverse event irrespective if a clinical event has occurred.

The investigator has the responsibility for managing the safety of individual patient and identifying adverse events.

Novartis qualified medical personnel will be readily available to advise on trial related medical questions or problems.

The occurrence of adverse events must be sought by non-directive questioning of the patient at each visit during the study. Adverse events also may be detected when they are volunteered by the patient during or between visits or through physical examination findings, laboratory test findings, or other assessments.

Adverse events must be recorded in the Adverse Events CRF under the signs, symptoms or diagnosis associated with them, accompanied by the following information (as far as possible) (if the event is serious refer to Section 10.1.2):

1. The severity grade.

- mild: usually transient in nature and generally not interfering with normal activities
- moderate: sufficiently discomforting to interfere with normal activities
- severe: prevents normal activities
- 2. Its relationship to the study treatment. If the event is due to lack of efficacy or progression of underlying illness (i.e. progression of the study indication) the assessment of causality will usually be 'Not suspected'. The rationale for this guidance is that the symptoms of a lack of efficacy or progression of underlying illness are not caused by the trial drug, they happen in spite of its administration and/or both lack of efficacy and progression of underlying disease can only be evaluated meaningfully by an analysis of cohorts, not on a single patient.
- 3. Its duration (start and end dates) or if the event is ongoing, an outcome of not recovered/not resolved must be reported.
- 4. Whether it constitutes a SAE (see Section 10.1.2 for definition of SAE) and which seriousness criteria have been met

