#### 2.8.1 Adverse events (AEs)

All information obtained on adverse events will be displayed by treatment sequence and patient.

All treatment emergent AEs will be summarized and listed.

AEs starting on or after the time of the first inhalation of study drug and until 30 days after the last inhalation will be classified as a treatment emergent AE. Any AEs that started during the study after signing informed consent and before the time of the first inhalation of study drug will be classified as a prior AE and will not be included in tabulations of the treatment emergent AEs.

The following treatment emergent AE summaries will be produced:

- by treatment, system organ class and preferred term,
- by treatment, system organ class, preferred term, and maximum severity

Novartis	Confidential	Page 14 of 16
SAP Amendment 1		Study No. CQMF149G2203

suspected drug-related AEs by system organ class and preferred term, SAEs by system organ class and preferred term, and AEs leading to discontinuation of study-drug by system organ class and preferred term.

The number and percentage of patients with the most frequent AEs will be summarized by treatment.

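### After the dosing day, QMF149 events wait for a 30-day telephone call without medication review, while MF events are reviewed in clinic at 5 to 8 days

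*Protocol*

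**What the plan says.** Protocol Section 6.1.4 fixes the order of treatment: "All patients will receive an inhaled single dose of MF TH 100 μg on Day 1", with QMF149 following on Day 6. Table 8-1 gives the Day 6 visit a window of -0/+3 days. It marks AE/SAE, physical examination, vital signs and medication review there.

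For a child who completes, the only later column in Table 8-1 is Follow Up (Day 36). Its footnote reads "This would occur 30 days after last study treatment", and Section 9.2 describes the contact: "All treated patients should have a safety follow-up call conducted 30 days after last administration of study treatment". The column marks only AE/SAE and the call itself. The row "Prior/ concomitant medication review" is marked at Screening, Day 1, Day 6 and Early Termination, and is blank at Follow Up.

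Two general rules bear on this. On adverse events, Section 10.1.1 states: "The occurrence of adverse events must be sought by non-directive questioning of the patient at each visit during the study". On medications, Section 6.2.1 states that everything "administered after the patient was enrolled into the study must be recorded in the concomitant medications" and non-drug therapies pages.

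Safety and tolerability of QMF149 is a secondary objective (protocol Table 2-1, SAP Table 1-1). SAP Section 2.8.1 plans AE tables by treatment and adds: "The number and percentage of patients with the most frequent AEs will be summarized by treatment".

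**The concern.** A short, mild event two or three days after a dose is easier to report and date within a week than after a month. Under this schedule the MF interval gets the early clinic review. The QMF149 interval, which the safety objective is about, gets the late telephone call. Rescue or other medication taken at home after MF is reviewed on Day 6. For a completer, the same use after QMF149 has no scheduled review, although a medication query can bring out an event that general questioning misses.

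The consequence is twofold. The safety description of QMF149 after the clinic day rests on recall over about four weeks. The by-treatment AE tables also set side by side two sets of events that were sought at different delays, by different means and over windows of different length, and the SAP makes no allowance for this.

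**Working it through.** **Inputs**
- MF dose: Day 1 (protocol Section 6.1.4).
- Day 6 visit: window -0/+3, so Days 6 to 9 (Table 8-1).
- Washout: 4 to 7 days (Section 3.1.1).
- Follow-up call: 30 days after the last dose (Section 9.2 and the footnote to Table 8-1); column label Day 36.
- Dosing-day measurements: Table 16-5, Sections 8.4.1 and 8.4.2.

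**Step 1: reproduce the plan's own timing.** Day 6 + 30 = Day 36, as labelled. Clear days between doses are 6 - 2 = 4 to 9 - 2 = 7, which matches the stated washout.

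**Step 2: time from dose to the next scheduled AE review after the clinic day.**
- MF: 6 - 1 = 5 days to 9 - 1 = 8 days, in clinic.
- QMF149: 30 days, by telephone (Day 36, or Day 9 + 30 = Day 39 if dosed at the end of the window).

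**Step 3: difference in delay.** Take an event that starts after the child goes home but before the MF review would have taken place.
- Extra delay after QMF149 = 30 - 8 = 22 days to 30 - 5 = 25 days.
- Ratio of the two intervals = 30/8 = 3.75 to 30/5 = 6.

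This takes the 30-day rule as governing. If the call were held to Day 36 after a Day 9 dose, it would fall 27 days post-dose, and the lower figure would be 27 - 8 = 19 days.

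**Step 4: what each contact contains (Table 8-1).**

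| | After MF (Days 6 to 9) | After QMF149 (30 days) |
|---|---|---|
| Mode | Clinic | Telephone |
| AE/SAE | Yes | Yes |
| Examination, vital signs | Yes | No |
| Medication review | Yes | No |

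Table 8-1 also lists a telephone call before the Day 6 visit. Its footnote makes it a reminder to withhold medication, and no separate AE query is tied to it. Section 9.2 mentions a completion visit, but Table 8-1 has no such column.

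**Step 5: the dosing day itself.** Table 16-5 gives QMF149 four post-dose safety time points: vital signs at 15 minutes and 1 hour, ECG at 20 minutes and laboratory tests at 6 hours. It gives MF none; Day 1 has pre-dose vital signs only. Here the imbalance runs the other way.

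**Step 6: the reporting window.** SAP Section 2.8.1 counts events from the first inhalation to 30 days after the last, and gives no rule for assigning an event to MF or QMF149. If events go to the most recent dose (an assumption), MF has 5 to 8 days and QMF149 has 30. The longer window tends to raise the crude QMF149 count.

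**The case against.** The other side has several sound points.

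- **Acute events are better covered after QMF149.** Step 5 confirms it. This limits the concern to events that start after the child leaves the clinic; the extra monitoring ends 6 hours after the dose.
- **Other provisions exist.** Events may be volunteered between visits (Section 10.1.1), patients are told to notify staff of new medications (Section 6.2.1), drugs used to treat AEs must be recorded (Section 6.6.2), and the Day 36 call does ask about AEs. These reduce any loss by an unknown amount. None is a scheduled early contact, and recording a drug that treats a known event does not bring out an event nobody has mentioned.
- **The consequence is limited.** The objective is to evaluate QMF149, not to test its AE rate against MF. There is no AE hypothesis, medications are only listed, and with one fixed sequence any AE contrast is confounded with period whatever the contact schedule. That stands, and it is why the point concerns the quality of description and does not touch the primary PK comparison.

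A reader might go further and infer that the AE tables understate QMF149 events. The documents do not support that. Later questioning would tend to lower the QMF149 count, while closer dosing-day monitoring and the longer window would tend to raise it. Nor can the loss be put as a percentage: that needs a forgetting rate, and neither document gives one.

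**Conclusion.** The point holds for events that start after the dosing day. For these, the first scheduled AE questioning comes 30 days after QMF149 by telephone, against 5 to 8 days after MF in clinic, a difference of 22 to 25 days. The medication-review row is blank at the Day 36 call, which does not match the recording duty in Section 6.2.1. Both statements follow from the schedule. They assume that visits take place as planned, that the 30-day rule governs the call, and that the event was not volunteered earlier.

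The broader statement that early QMF149 events are captured less well than early MF events does not hold, because in the hours on site the reverse is true for vital signs, ECG and laboratory findings. The net direction and size of any bias in the by-treatment tables cannot be determined from the documents. What can be said is that those tables rest on unequal ascertainment and unequal windows, and that neither document says so.

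**What to change.** 1. **Table 8-1:** mark "Prior/ concomitant medication review" for the Day 36 call, so that the schedule agrees with Section 6.2.1. This needs no extra contact. Section 9.2's mention of a completion visit should be reconciled with the table at the same time.
2. **One added contact:** a short AE and medication telephone call 5 to 8 days after the QMF149 dose, with the same non-directive questions, keeping the Day 36 call. It costs a small protocol amendment and about 24 to 32 calls by existing site staff, with no blood sample or visit. The QMF149 AE count may rise slightly. A call still differs in mode from the clinic visit after MF, so the match is closer but not complete.
3. **SAP Section 2.8.1:** show by-treatment AEs by onset date within the same post-dose window for both treatments, for example each child's own interval between doses. Include events seen on site and events volunteered between visits, because selecting events by how they were elicited would drop both. List later QMF149 events separately, and state that ascertainment and period differ between treatments. This is wording and programming only.

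If the added call is not accepted, items 1 and 3 remain worth making, with the difference in ascertainment reported as a limitation.

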10.1 Definition of adverse events and reporting requirements

10.1.1 Adverse events

An adverse event (AE) is any untoward medical occurrence (e.g. any unfavorable and unintended sign [including abnormal laboratory findings], symptom or disease) in a patient or clinical investigation patient after providing written informed consent for participation in the study. Therefore, an AE may or may not be temporally or causally associated with the use of a medicinal (investigational) product.

In addition, all reports of intentional misuse and abuse of the product are also considered an adverse event irrespective if a clinical event has occurred.

The investigator has the responsibility for managing the safety of individual patient and identifying adverse events.

Novartis qualified medical personnel will be readily available to advise on trial related medical questions or problems.

The occurrence of adverse events must be sought by non-directive questioning of the patient at each visit during the study. Adverse events also may be detected when they are volunteered by the patient during or between visits or through physical examination findings, laboratory test findings, or other assessments.

Adverse events must be recorded in the Adverse Events CRF under the signs, symptoms or diagnosis associated with them, accompanied by the following information (as far as possible) (if the event is serious refer to Section 10.1.2):

1. The severity grade.

- mild: usually transient in nature and generally not interfering with normal activities
- moderate: sufficiently discomforting to interfere with normal activities
- severe: prevents normal activities
- 2. Its relationship to the study treatment. If the event is due to lack of efficacy or progression of underlying illness (i.e. progression of the study indication) the assessment of causality will usually be 'Not suspected'. The rationale for this guidance is that the symptoms of a lack of efficacy or progression of underlying illness are not caused by the trial drug, they happen in spite of its administration and/or both lack of efficacy and progression of underlying disease can only be evaluated meaningfully by an analysis of cohorts, not on a single patient.
- 3. Its duration (start and end dates) or if the event is ongoing, an outcome of not recovered/not resolved must be reported.
- 4. Whether it constitutes a SAE (see Section 10.1.2 for definition of SAE) and which seriousness criteria have been met
- 5. Action taken regarding with study treatment.
- 6. Its outcome (not recovered/not resolved; recovered/resolved; recovering/resolving; recovered/resolved with sequelae; fatal; or unknown)

All adverse events must be treated appropriately. Treatment may include one or more of the following:

- Drug interrupted/withdrawn
- Concomitant medication or non-drug therapy given
- Patient hospitalized/hospitalisation prolonged
- No action taken (i.e. further observation only)

Conditions that were already present at the time of informed consent should be recorded in medical history of the patient.

Adverse events (including lab abnormalities that constitute AEs) should be described using a diagnosis whenever possible, rather than individual underlying signs and symptoms.

To ensure patient safety, every adverse event, occurring after the patient has provided informed consent and until end of the trial for each patient must be reported.

Adverse event monitoring should be continued for at least 30 days following the last dose of study treatment.

Abnormal laboratory values or test results constitute adverse events only if they fulfill at least one of the following criteria:

- they induce clinical signs or symptoms
- they are considered clinically significant
- they require therapy

Clinically significant abnormal laboratory values or test results must be identified through a review of values outside of normal ranges/clinically notable ranges, significant changes from baseline or the previous visit, or values which are considered to be non-typical in patients with the underlying disease. Alert ranges for laboratory and other test abnormalities are included in Section 16.1.

Once an adverse event is detected, it must be followed until its resolution or until it is judged to be permanent, and assessment must be made at each visit (or more frequently, if necessary) of any changes in severity, the suspected relationship to the study drug, the interventions required to treat it, and the outcome.

Information about common side effects already known about the investigational drug can be found in the Investigator Brochure (IB).

